9.1 Study design

The study is a randomized waitlist controlled trial of a sleep improvement app. The present study design is summarized in Figure 1. We decided to use a between-group design as we want to determine the effect of the sleep improvement app vs. not using anything, as the study app is aiming to improve subjective sleep quality in order to prevent progression to clinical relevant sleep problems (primary prevention). Participants will be randomly assigned to the Sleep Improvement App intervention or the waitlist condition. Online assessments will take place at Baseline (0 weeks), 6 weeks (during the intervention), and 12 weeks (after intervention).

9.2 Randomization and allocation concealment

This study will use simple randomization with an allocation ratio of 1:1, as recommended for large randomized controlled trials. Randomization will be conducted by an automated online system; hence the research team will be unable to influence randomization and have no access to future allocations.

9.3 Blinding

[figure not shown]
Assessments will be self-reported and carried out online, and the research team will be blinded to outcomes during the trial. Participants will be informed of their randomization outcome by an automatic email, and hence they will not be blinded to treatment allocation. It is notable that the study sponsors will not have any contact with research participants and will therefore be unable to bias the allocation or assessments. If participants do contact the team and reveal the allocation, the absence of assessments carried out by an investigator prevents any biases.

9.4 Type/Design of study

Naïve participants will be consecutively enrolled into the trial and randomized into either the wait-list condition or Sleep Improvement App-condition, provided that all inclusion and exclusion criteria are met and consent is given to use their data according to data privacy regulations. A participant information document with consent form will be provided with page-turning function. Participant has to agree that his/her data will be used in this study by clicking “yes, I agree” or “no I don’t agree and do not want to participate”.

Eligible participants will receive written information about all relevant aspects of the study and that their participation in the study is voluntary and they have the right to refuse or withdraw their consent at any time without negative consequences. The study has been registered with ClinicalTrials.gov (210915DSDT). This paper contains modifications, which will be submitted to the Ethics Committee for approval prior to implementation. The current and further amendments will be documented in detail in the ClinicalTrials.gov registry. On the consent form, participants will be asked if they agree to the use of their data in case of withdrawing from the trial. Participants will also be asked for permission for the research team to share relevant data with people from SleepScoreLabs and ResMed taking part in the research or from regulatory authorities, where relevant. This trial does not involve collecting biological specimens for storage.

9.4.1 CONSORT Study Flow Diagram

9.4.2 Primary Endpoint

Statistically significant improvement in subjective sleep quality measured using a validated questionnaire between active sleep-improvement condition through the Dein Schlaf. Dein Tag. App and the waitlist condition comparing baseline with 6 weeks and 12 weeks measures.

- Self-report sleep parameters: Sleep Quality score (SQ) of the SF-B (9 Items)

9.4.3 Secondary Endpoints

Improvements in sleep metrics between app condition and waitlist condition comparing baseline with 6 weeks and 12 weeks measures

Note, given the dynamic and personalized nature of the intervention and its potential impact on various self-assessed goals, we have chosen multiple secondary endpoints that we expect to see statistically significant sleep improvements in depending on baseline self-reported sleep parameters, including the following:

- Health measures including overall sleep problems, feeling of being refreshed in the morning, mental health stress (PSQI, PSS, SF-12, SF-B)
- Objective sleep parameters (only app condition): Total sleep time, sleep onset latency, wake after sleep onset, sleep efficiency.
- Self-reported app-based items in app condition group.

9.4.4 Study population

This research aims to target a non-clinical population with subclinical sleep disturbances that is interested in improving their sleep. To ensure we recruit a non-clinical sample, we will exclude users who have indicated they have a diagnosed sleep disorder as well as those identified as being at high risk of a sleep disorder based on validated screening tools. This research has no specific recruitment goals with respect to race or ethnicity and will not base participant eligibility on such criteria. However, this information may be recorded as part of the data collected.

Inclusion criteria:

- iOS user, or user of one of the following: Samsung Galaxy S7 Edge and S7, S8, S8+, S9, S9+, S20, S20 FE, S20+, S21 Ultra Samsung Galaxy Note 8 and 9
- Regensburg Insomnia Scale (poor sleep indicated by a score of 13-24, excluding those without sleep problems and those with probable insomnia disorder)
- ≥ 18 years old.
- Naive to the SleepScore Labs App
- Not included in other treatments around sleep
- Able to fully understand information on data protection and provide written informed consent

Exclusion criteria:

- Bedtime less than 6 hours
- Any of the following medical problems:
 - Untreated psychological disorder affecting sleep (e.g., depression, anxiety disorders, bipolar disorder, schizophrenia)
 - Current severe medical conditions (e.g. chronic pain, cancer)
- Any of the following medications/substance use:
 - Prescription sleep medication or regular use of over-the-counter sleep medication
 - Medication for other conditions (e.g., anxiety, ADHD) that affect sleep, e.g. antidepressants, antipsychotics
- Consumption of 3+ units of alcohol on 4 or more nights per week
- Recreational or nightly drug use
- Pregnant or nursing mothers
- Shift work
- Travel across 2 or more time zones during study period
- Sleeping more than 7 nights not at home during study period
- Users who newly received a diagnosis of a sleep disorders
- Users who start sleep or other psychoactive medication during the study period

- Use of other Sleep Tracking App's during the study period

9.4.5 Study duration

Recruitment for the study will be rolling, Baseline Assessment is at week 0. A follow up is scheduled after 6 weeks and 12 weeks of both the app and waitlist group. The end of data collection is planned after 12 weeks from baseline of the last user included. Final intention to treat analysis of study data will subsequently be performed.

9.4.6 Withdrawal from the trial

Participants are free to withdraw from the trial at any time without giving any reasons. They will not have any negative consequences in the relationship to SleepScore Labs or ResMed. In the event that a user withdraws consent, the date and reason for termination – if provided – will be documented. For participants who drop out of the study, assessments that are part of the study design will be conducted only if the participants agree.

9.4.7 Compensation

All enrolled participants will receive 20 euros for completing each follow-up assessment including baseline, 6-weeks, and 12-weeks, paid at the end of the study. Regular use of the sleep app will be compensated with 50 Euros.

9.4.8 Sleep Measurement

The Dein Schlaf. Dein Tag. application powered by SleepScore includes a polysomnography-validated non-contact sleep monitoring technology employing inaudible sonar to monitor the movements and respiration of a participant in bed. A validation study of the sonar technology against gold-standard polysomnography showed high sensitivity (88%) and specificity (65%), exceeding agreement that is typically reported for actigraphy based devices ([Zaffaroni et al., 2019](#)).

Sleep measurement is achieved via a smartphone app, which have become ubiquitous in the last decade, eliminating the initial barrier to adoption represented by the cost and effort associated with purchasing a custom piece of hardware. The average emitted acoustic power is less than 75dB, well within the most stringent guidelines on sound exposure and the frequencies employed are above 18 KHz, above the audibility range of the vast majority of the adult population. The app utilizes a patented sensing technology and custom algorithms. Sleep monitoring can be achieved by placing a smartphone onto the bedside locker and starting the app. The app employs sophisticated algorithms to identify sleep stages: Wake (W), Light Sleep (N1, N2 sleep), Deep Sleep (N3 sleep), REM or Absence. The algorithms for the app technology were developed by using several hundred-night recordings from multiple subjects in their home consisting of concurrent measurements performed via a smartphone equipped with the Drive app and a ResMed S+ device respectively.

9.4.9 Intervention and Control

The Dein Schlaf. Dein Tag. App powered by SleepScore is a personalized and dynamic digital sleep improvement program offered via smartphone. The app begins with a brief

onboarding and registration process that informs the personalized sleep advice, followed by sleep improvement personalization goals including the following potential options: sleep longer, wake up less, fall asleep easier, sharpen my mind, recharge my body, stay asleep until morning, or perfect my sleep (improve SleepScore). Users are then asked to select health-related measures that are most important for them, the regularity of their bedtime, how often they exercise, common sleep disturbances, and overall self-reported sleep quality.

Based on the user's onboarding data and nightly objective sleep tracking data, the Dein Schlaf. Dein Tag. application powered by SleepScore provides personalized evidenced-based sleep advice and sleep education content founded in the principles of sleep hygiene and cognitive behavioural skills. Additional sleep improvement features embedded within the app include weekly sleep challenges, sleep sanctuary bedroom checks, sleep sounds, smart alarm, bedtime reminders, and sleep education blogs.

To increase user engagement and adherence to tracking and sleep improvement features, the application integrates contextual reinforcement strategies through daily and weekly prompts to encourage positive sleep health-related behaviours. These prompts include smartphone push notifications, in-app overlays, and emails providing sleep education content, sleep tips, individual sleep feedback, tracking/daily log reminders.

The app uses several behaviour change techniques to improve sleep-wake functioning, including the following:

Goal setting and planning. Goal setting is a key component to app onboarding and the advice engine. Users can select any of the following goals: sleep longer, wake up less, fall asleep easier, sharpen my mind, recharge my body, stay asleep until morning, or perfect my sleep (improve SleepScore). Users are then asked to select health-related measures that are most important for them, the regularity of their bedtime, how often they exercise, common sleep disturbances, and overall self-reported sleep quality. The app then uses criteria to give feedback to users when they are nearing or meeting sleep improvement criteria based on these goals.

Feedback and monitoring. The sleep history page shows retrospective SleepScore's in order to reduce false beliefs about sleep by providing objective sleep data. In relation to goals and planning, feedback on behaviour is provided based on the measurement of objective sleep and daytime behaviours logged in the log-your-day feature.

Shaping knowledge. We use advice and insights based on the sleep guide and log your day items with instructions on how to remove or reduce aversive stimuli (e.g., excessive caffeine intake, excessive pre-bed light, alcohol consumption, sedentary behavior) and improve stimulus control (e.g., only using bed for sleep and intimacy).

Natural consequences. Information about health consequences and the salience of insufficient or poor quality sleep are provided to users in the sleep guide and research articles summarized as blog posts.

9.4.10 Inclusion of users and baseline parameters

The investigator will inform eligible users about the study and the use of data. If the user is willing to participate, the informed consent form for data use will be handed out for signature. After signing by user and investigator, study relevant data will be reported after the participants has completed relevant questionnaires (see Annex1)

9.4.11 Assessments Table

Assessment	Baseline	6 weeks	12 weeks
Inclusion and exclusion criteria	X		
Demographics	X		
History	X		
Social status	X		
Self-report questionnaires (see Annex 1)	X	X	X
Assessment of objective sleep parameters via Dein Schlaf. Dein Tag App (each night)	X	X	X

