	
critical statistical test would be the interaction term between app condition and the waiting-list control group.
 
Objectively measured data will be analyzed using multi-level modeling (MLM) in a nested way (nights within participants), allowing for analyzing changes within the intervention (app) group. To evaluate changes in primary and secondary outcome measures assessed by validated scales at baseline, 6-weeks, and 12-weeks, we will compare within-group differences for each time-point using a t-test if normally distributed, or the Mann Whitney-U test for non-normally distributed continuous data. In addition, effect sizes for the changes within both groups (questionnaire data) and app group (objective sleep parameters) will be computed.

--	---

4. Amendments and updates

Amendment No. 1, Jan 26 2023

Amendment No. 2, Apr 28 2023

Section	Amendment or update detail	Reason
5 Milestones	Dates changed	Adapted according to preparation of study
9.4 Design	Deleted “written”, added “A participant information document with consent form will be provided with page-turning function. Participant has to agree that his/her data will be used in this study by clicking “yes, I agree” or “no I don’t agree and do not want to participate”.”	Electronic consent ensures that participants can follow a defined workflow and pathway and will be guided smoothly through the recruitment portal. This avoids that too many potential participants are being lost during the course of recruitment.
9.4.1	Adapted flowchart: Informed Consent – then baseline assessment – then randomization	Now follows the routine in study practice. Before the randomization should have occurred before the baseline assessment. Since randomization means access to the app for the “app group”, the timepoint of filling out the baseline questionnaire could have been after first app usage. This will be avoided when doing baseline before randomization and app download.
9.5.1 Data	Deleted Munich Chronotype Questionnaire	Conversion into electronic format problematic; would have compromised the outcomes

9.5.1 Data	Deleted Landecker Inventar zur Erfassung von Schlafstörungen (LISST)	Study flow and assessment of participants for eligibility in the e-portal required a combination of in-/exclusion criteria with the LISST to ensure all screening criteria could be met. LISST is not required to be applied as a separate questionnaire.

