9.7.1 Data management	Deleted [...],“forwarded to SleepScore, there combined with objectively measured sleep data, and then securely shared with ResMed where it will be stored for 10 years.” Added: “Objective sleep data from the app as collected and controlled by SleepScore Labs and self-reported questionnaire data as collected by a vendor on behalf of ResMed Objective sleep data from the Dein Schlaf. Dein Tag. App as specified in this protocol, and without personal identifiers will be send to vendor, combined with self-reported questionnaire data by vendor and equipped with new identifiers to result in a de-identified set of study data. [...]shared with Sleepscore Labs for joint analysis.” Added: “De-identified study data will be stored at ResMed for 10 years.”	Changes were necessary to be compliant with EU-GDPR. Processes had to be restructured to prevent ResMed from potentially getting access to personal data of study participants.
Annex 1	Deleted LISST	Not required as separate questionnaire. Accurate recruitment of participants through automated electronic assessment made a fusion of eligibility criteria necessary.
Annex 1	Deleted Munich Chronotype Questionnaire	Conversion into electronic format problematic; would have compromised the outcomes
Inclusion criteria	Added “Samsung Galaxy S7 Edge and S7, S8, S8+, S9, S9+, S20, S20 FE, S20+, S21 Ultra Samsung Galaxy Note 8 and 9”	Increasing the number of active users of the application by also allowing other devices which have been validated to deliver a similar performance in running the app.

5. Milestones

Milestone	Planned date
Start of enrolment	January 2023 (actual)
End of enrolment	May 2023 (anticipated)
Final results	July/August 2023 (anticipated)

6. Rationale and background

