9.7 Data management

Applicable national and international legal requirements for data handling and data archiving will be met. Participant study materials including recruitment materials, participant informed consent documents (PICF), study withdrawal forms, and study progress will be collected using an EU data center of Forsta/Decipher which is GDPR compliant, ISO 27001 certified, with SOC2 accredited data centers.

Objective sleep data will be collected using the Dein Schlaf. Dein Tag. application, and stored within an EU data center of the Microsoft Azure cloud system, an ISO 27001 certified and SOC 1, SOC 2, and GDPR compliant cloud service provider. Self-reported questionnaire data will be captured using an EU data center of Forsta/Decipher which is GDPR compliant, ISO 27001 certified, with SOC2 accredited data centers. Objective sleep data is encrypted in transit and at rest and additionally, personally identifiable information is hashed before being stored in the database. Access to databases for data analysis which include person identifiable information is limited to approved administration staff and is locked to the corporate IP address in the EU.

Personal information identifiers are separated from measurements so that employees of SleepScore Labs International LTD can work with accordance of least privilege to perform adequate work duties. Authentication controls are also implemented to protect customer data using passwords and usernames – external parties do not have any authentication services. Upon completion of data collection, de-identified objective data from Microsoft Azure cloud system and self-reported Forsta/Decipher data will be merged into a GDPR compliant data repository. Azure Data Factory will be used to combine the data, with processed data being stored in a Microsoft Azure SQL Server hosted in the EU. Access to this repository, which is required for analysis, will be limited to specific EU-based employees.

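### Objective sleep has neither a pre-app baseline nor a waitlist comparator, so its within-app change should be reported as descriptive and not as evidence that the app improves objective sleep

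*Protocol*

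**What the plan says.** **Source of the data.** Protocol 9.7 states: "Objective sleep data will be collected using the Dein Schlaf. Dein Tag. application". Protocol 9.4.3 restricts the outcomes to one arm: "Objective sleep parameters (only app condition): Total sleep time, sleep onset latency, wake after sleep onset, sleep efficiency". SAP 3.2 agrees, and SAP 4.1 defines the waitlist as a group that does not use the app.

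**Timing of access.** The reason given in protocol section 4 for reordering the flowchart includes "Since randomization means access to the app" for the app group. It places the baseline questionnaires before both randomisation and download. SAP 4.2 confirms the order: consent, baseline, randomisation. Protocol 9.4.4 requires participants to be new to the app.

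**Baseline label.** Protocol 9.4.11 marks "Assessment of objective sleep parameters via Dein Schlaf. Dein Tag App (each night") under Baseline as well as at 6 and 12 weeks. SAP 5.1 lists objective sleep variables with the baseline characteristics.

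**Tracking and advice.** Under protocol 9.4.9, use starts with onboarding and goal selection. Advice then draws on onboarding data and "nightly objective sleep tracking data, the Dein Schlaf. Dein Tag. application powered by SleepScore provides personalized evidenced-based sleep advice". Among the behaviour-change techniques, "feedback on behaviour is provided based on the measurement of objective sleep and daytime behaviours logged in the log-your-day feature".

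**Question and analysis.** SAP 3.1 and 8.2 plan comparisons of baseline with 6 and 12 weeks within the app arm, and SAP 7 specifies a multilevel model with nights nested in participants. SAP 3, however, gives the study's purpose as finding out whether the app improves objective as well as subjective sleep. Protocol 9.4.3 puts the objective parameters under a lead-in about improvements between app and waitlist. The limitations section (9.11) mentions only variation in app use.

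**The concern.** The instrument that measures objective sleep is also the intervention. Bringing the questionnaire baseline forward, ahead of randomisation and download, protects the questionnaires. It cannot protect the objective outcomes, because nothing is recorded until the app is installed.

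Two consequences follow. The reference period is post-download, so any early benefit is subtracted from the change. There is also no concurrent control, so anything else that moves sleep over 6 or 12 weeks is counted in the change. A report that follows SAP 3 and protocol 9.4.3 could then present a significant within-app change as an effect of the app, which the design cannot support. The error could go either way: early benefit in the reference nights hides improvement, while drift can create or mask it.

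**Working it through.** The documents give no drift, standard deviation or early-benefit figure for objective sleep, so there is no figure of the plan's own to reproduce. The check is a reading of the sequence, an identity, and an illustration on stated assumptions.

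**1. Can a pre-download objective measure exist?** Recording needs the app (9.7). The app comes with randomisation (section 4), after the baseline assessment (SAP 4.2), in people who have not used it before (9.4.4). So none can exist, and the objective Baseline must be nights after download.

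**2. Are those nights exposed to the intervention?** Onboarding and goal setting come first, feedback on tracked sleep is itself a technique, and no advice-free run-in is described (9.4.9). Some exposure is therefore plausible. However, advice built on tracking data cannot precede the first tracked night, and no passage dates the first advice. Exposure is inferred and its amount is unknown.

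**3. What does the change estimate?** Let B be underlying sleep, A the app effect at follow-up, f the share of A already present in the reference nights, and D0 and D6 the non-app drift at reference and week 6.

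- reference mean = B + fA + D0
- week-6 mean = B + A + D6
- expected change = A(1 − f) + D, with D = D6 − D0

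That is one contrast with three unknowns. A multilevel model handles the clustering of nights but estimates the same quantity. An observed change of 10 minutes fits A = 10, f = 0, D = 0. It fits A = 20, f = 0.5, D = 0. It also fits A = 0, D = 10.

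With A assumed to be 10 minutes, the expected change in minutes is:

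| f | D = −10 | D = 0 | D = +10 |
|---|---|---|---|
| 0 | 0 | 10 | 20 |
| 0.25 | −2.5 | 7.5 | 17.5 |
| 0.5 | −5 | 5 | 15 |

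**4. How readily could drift alone give significance?** As a simplified illustration, take one paired t-test, two-sided 5%, A = 0 and drift d in SDs of the change score. The noncentrality is d√n with n − 1 degrees of freedom. The n values are the per-group sizes in protocol 9.6: 150 stated as required and 300 planned.

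| d (assumed) | n = 150 | n = 300 |
|---|---|---|
| 0 | 5% | 5% |
| 0.10 | 23% (d√n = 1.22) | 41% (1.73) |
| 0.20 | 68% (2.45) | 93% (3.46) |

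This is not the planned model, and n = 300 supposes that every app participant supplies nights in both periods.

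**5. Where could drift come from?** Enrolment runs from "January 2023 (actual") to an anticipated May 2023, so a seasonal trend over 12 weeks need not average out. Participants are selected on an insomnia score of 13–24 (9.4.4). That scale is self-rated and the range is cut at both ends, so neither the presence nor the direction of regression to the mean in the app's measures can be read from the documents. Adaptation to tracking is possible but not quantified.

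**The case against.** The strongest reply is that the limit is already disclosed. The protocol's objectives, its 9.4.3 and 9.8, and SAP 3.1, 3.2, 7 and 8.2 all confine objective sleep to the app arm. SAP 8.2 is a valid test of whether sleep changed within that arm and makes no causal claim. The sentence in SAP 3 is background. Measuring only app users is also a coherent choice when the comparison is with using nothing and tracking feedback is part of the intervention. All of this stands except the suggestion that the causal framing is confined to one background sentence: the lead-in to protocol 9.4.3 has it too.

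A reader might go further and infer that the documents contradict themselves, or that the reference nights are shown to be on treatment. Neither is supported. Only the questionnaires are placed before download, and the Baseline mark can be read as the start of nightly recording. Exposure on those nights rests on the order of steps.

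A reader might also infer that the plan never defines its baseline, week-6 and week-12 nights. The readable text does not define them, but the flow diagrams and SAP tables are not shown and may do so, so that part is conditional. A diagram could not supply pre-download recordings or waitlist data.

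Finally, the comparison with existing data in SAP Annex II gives context but is not a concurrent control.

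**Conclusion.** The point holds as a minor one about what may be concluded. Objective sleep has a post-download reference and no comparator, so the planned change cannot answer whether the app improves objective sleep. The wording of SAP 3 and protocol 9.4.3 asks more than the design gives.

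The size of any bias is unknown. On the assumed values above, a true 10-minute effect could appear as anything from −5 to +20 minutes. Drift of 0.1 to 0.2 SD with no app effect would be significant in 23% to 68% of trials at n = 150 and in 41% to 93% at n = 300. These figures show sensitivity; they do not estimate what will happen here.

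It would be wrong to infer that the SAP 8.2 test is invalid or that the trial's main result is compromised. The first is a legitimate within-arm test. The SF-B primary endpoint is randomised, controlled and measured before app access, so it is unaffected.

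**What to change.** 1. **SAP 3 and protocol 9.4.3:** limit the app-versus-waitlist efficacy question to the questionnaires. State that the objective parameters are descriptive changes within the app arm and will not be attributed to the app.
2. **Protocol 9.4.11 and SAP 5.1:** relabel the objective baseline as app arm only, first tracked nights after download.
3. **SAP 7 and 8.2:** report week 6 and week 12 minus reference from the planned multilevel model, with 95% confidence intervals, as descriptive. Unless the figures not shown already do so, fix the reference, week-6 and week-12 windows before analysis from a single time origin, for example days since download. Keep all other tracked nights in the model in a category called other, so that none are discarded (SAP 6.1).

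**Cost.** These are wording changes and window definitions, with no new data. The sponsor gives up an objective-sleep efficacy claim that the design cannot support. Early benefit may still be subtracted, because the reference remains post-download. A short reference window limits exposure but is noisier: treating nights as independent, the night-to-night standard error of its mean is √(7/3) = 1.53 times larger with 3 nights than with 7.

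An origin at download also needs a check against protocol 9.4.5: "The end of data collection is planned after 12 weeks from baseline of the last user included". If download comes d days after baseline, a window ending on day 84 from download ends on day 84 + d from baseline. That could fall outside data collection for the last participants, so report how many have no nights in each window.
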